b) Patient follow-up

Analyses will be carried out locally or off-site depending on the examinations concerned:

Off-site analyses (CHU Nantes): II2, II4, II6, II8, II10, GM-CSF, TNF-alpha, INF-beta, neurofilament. All these analyses can be performed using a 5 ml blood tube for all the analyses (i.e. a total of 60 ml of blood taken, taking into account the safety sample kept on the investigator's site). The principles of the LuminexTM assay and the Patrol test are explained in appendix J.

Local tests: blood count, arterial blood gases (pH, pO₂, pCO₂, HCO₃), lactates, blood ionogram (Na, K, Cl, Urea, Creatinemia, Ca), troponin, CRP, procalcitonin.

Local examination: 12-lead electrocardiogram

Neurological analysis using the CPC score will be carried out by telephone by an expert blinded to the randomisation group (psychologist carrying out a semi-directive interview, blinded to the randomisation group).

Flow Chart :

	Inclusion	J0	J1	J2	Jn	J90
Eligibility: check the study's eligibility criteria	X					
Informing the next of kin with a cooling-off period	X					
No-objection search	X					
Demographic data	X					
Randomisation		X				
Patient characteristics	X					
Data : coronary angiography	X					
Data: ventilation	X	X	X	X	X	
Biology	X	X	X	X		
Electrocardiogram	X		X	X		
Clinical evaluation	X		X	X	X	X
Treatments administered		X	X	X	X	
Definitive extubation					X	X
Living / Deceased		X	X	X	X	X
Blind neurological assessment by a psychologist						X

D0 corresponds to the start of the hypothermia procedure.

Jn corresponds to discharge from intensive care

B. Description of measures taken to reduce and avoid bias

1. Prize draw

This randomisation will be carried out directly on the electronic observation notebook provided (see Data collection). Randomisation will be carried out according to a 1:1 ratio with blocks of variable size, as the study will be open-label. No stratification factors will be taken into account. Randomisation will be generated by the CIC INSERM 1415 biometrics unit, which is independent of the patient recruitment process. It will be carried out within a time window of 6 hours, the end of which will correspond to the end of the CCT 32.5-33.5 period (i.e. between H18 and H24). This delayed randomisation will allow only patients alive at the end of the 32.5-33.5 CCT period to be randomised, and not patients who died during the first phase (e.g. progressing to refractory shock).

2. Blinding method

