- Patient managed for cardiac arrest in shockable rhythm on arrival of emergency services and successfully resuscitated.

- Persistent coma on admission to intensive care (Glasgow score less than or equal to 8) in the absence of sedation. If the patient is sedated on admission to intensive care, the Glasgow score used will be the last score assessed by the doctor who provided pre-hospital care for the patient.
- Technical implementation of the CCT 32.5-33.5 with a specific thermoregulation device.

B. Criteria for non-inclusion of research subjects

- No-flow time > 10 minutes (period between the onset of cardiac arrest and the start of external cardiac massage).
- Low-flow time > 60 minutes (period between the start of external cardiac massage and recovery of haemodynamically effective cardiac activity).
- Major haemodynamic instability (dose of Noradrenaline and/or Adrenaline > 1 µg/kg/min to maintain MAP > 65 mmHg).
- Time between onset of cardiac arrest and start of induction of targeted thermal control greater than 5 hours.
- Moribund.
- Presence of histologically confirmed Child C cirrhosis.
- Taking an IL6 receptor inhibitor (tocilizumab or Ro-Actemra®).
- Patient on corticosteroid treatment (dose > 5mg prednisolone equivalent).
- Minors (<18 years)
- Pregnant, parturient or breast-feeding women.
- Patient hospitalised without consent and/or deprived of liberty by court order
- Patient under guardianship or trusteeship
- Prior inclusion in a research protocol with a random draw, and for which the primary endpoint is the bioassay of interleukin 6
- No social security
- Refusal of the trusted support person or the patient

C. Recruitment procedures

Recruitment will take place within the intensive care unit of the CHD Vendée. It is planned to include 60 patients admitted to the intensive care unit following a RTA, presenting a shockable rhythm on the arrival of the emergency services and justifying targeted temperature control between 32.5° and 33.5°C, after reading the information letter and obtaining the non-opposition of the trusted support person. The patient's non-opposition will be collected after reading the information letter.

D. Pre-hospital care

As this is a routine care study, no changes will be made to pre-hospital management. In particular, there is no published study showing any benefit from early CCT between 32.5 and 33.5°C compared with a few hours later. (87, 94, 95).

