The primary endpoint will be analysed using a linear mixed model. If necessary, the data will be transformed beforehand.

Analysis of secondary endpoints

Secondary endpoints associated with a binary variable will be analysed using Fisher's exact test.

Secondary endpoints associated with a quantitative variable will be analysed using the same strategy as for the primary endpoint, using Student (or Wilcoxon) tests if the data are not repeated.

Finally, the parameters of the repeated measurements will be analysed using mixed models.

B. *Expected number of people to be included in the research, and expected number of people in each research location with statistical justification*

The headcount calculation is based on the work of Borm (99) and Vickers (100).

In this trial, the primary endpoint (interleukin 6 levels) is measured repeatedly. To calculate the number of patients required, the following parameters are required:

- The standard deviation of the interleukin 6 assay was set at 40 pg/ml.
- The main hypothesis is that a high heating rate ($>0.5^{\circ}\text{C}/\text{h}$) leads to an increase in inflammatory phenomena measured by IL6. In this case, according to previous studies (101) the mean level of IL6 expected in the slow rewarming group will be 100 pg/ml.
- A 15% increase (superiority analysis) in these phenomena is assumed (i.e. an IL6 level of 115 pg/ml in the RR group compared with 100 pg/ml in the RL group).
- The correlation between 2 measurements of interleukin 6 in the same subject was set at 0.85. This correlation was estimated by the manufacturer at 0.89, but we have chosen to adopt a slightly lower value, as a conservative approach.
- The errors of the first and second kind were set at 5% and 10% respectively.

If the trial were planned with a single interleukin 6 assay, it would be necessary to include 151 patients per group.

Taking into account a measurement of interleukin 6 at inclusion, and considering that the correlation between the assessments at inclusion and at H32 was 0.85, the number of patients was reduced to 42 per group.

Taking into account the fact that there were 2 intermediate assessments (H12, H24), and that the correlation between the assessments was 0.85, the number of patients was reduced to 25 per arm.

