Taking into account an estimated 20% of patients who may have been included but not randomised (patients who died or progressed to refractory shock despite treatment), the plan is to include 30 patients per group, i.e. a total of 60 patients.

C. *Expected level of statistical significance*

All statistical tests will be carried out with a significance level of 5%.

D. *Method for taking into account missing, unused or invalid data*

A second serum sample from each analysis will be kept locally after the first sample is sent to the laboratory (Nantes University Hospital) carrying out the centralised analyses, so that a "safety" sample can be sent in case the first sample is accidentally lost or destroyed.

Randomisation immediately before the start of the warm-up procedure will avoid missing data for the primary endpoint (Interleukin 6 assay).

E. *Managing changes to the initial strategy analysis plan*

The statistical analysis plan will be finalised when the database is frozen.

F. *Choosing the people to be included in the analyses*

The analysis will be carried out on an intention-to-treat basis.

VI. Justification for requesting validation of research in routine care

In accordance with the decree of 9 March 2007 and taking into account all the elements presented in the project, the person responsible for the research qualifies it as **research in routine care**, since :

- ✓ All procedures and protocols for targeted temperature control between 32.5 and 33.5°C are carried out as usual.
- ✓ The aim is to evaluate combinations of procedures and medical strategies for prevention and diagnosis (protocol for targeted temperature control between 32.5 and 33.5°C, determination of rewarming rate) that are standard practice, i.e. that are the subject of a professional consensus in compliance with their indications.
- ✓ This research does not focus on techniques or strategies that are either innovative or obsolete.
- ✓ The research compares two medical strategies (determining a fast or slow rate of rewarming during a period of targeted temperature control between 32.5 and 33.5°C), neither of which can, in the current state of knowledge, be considered superior to the other in terms of safety and efficacy. In fact, the North American recommendations do not specify a target heating rate. They only advise avoiding

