These documents are :

- Protocols and annexes, any amendments,
- Information leaflets and objection forms
- Individual data (authenticated copies of raw data),
- Follow-up documents,
- Statistical analysis,
- Final report of the study.

At the end of the period of practical use, all the documents to be archived, as defined in the CHD Vendée's procedure for filing and archiving documents relating to biomedical research, will be transferred to the archiving site (CHD Vendée Clinical Research Centre) and will be placed under the responsibility of the establishment responsible for the research for 15 years after the end of the study, in accordance with institutional practices.

They may not be moved or destroyed without the agreement of the institution responsible for the research. At the end of the 15-year period, the institution responsible for the research will be consulted for destruction. All data, documents and reports may be audited or inspected.

XI. Financing and insurance

A. Study budget

Insofar as this trial is a routine care study, medical procedures will not be reimbursed. The expected duration of the study is 3 years for 1 centre. The unit cost grid by profession published and updated by the DGOS Bureau PF4 in 2014 was used. Thus, the costs associated with this research are as follows:

Estimate based on 50 randomised patients.

- Time for the psychologist to carry out blind telephone interviews with the randomisation group at D90 (2 hours for 50 patients at €38/hour) 3 800 €
- Data management :

• Data management time :	8 000 €
• Statistical analysis :	4 000 €
• Stationery for information and opt-out letters to patients or their relatives, bedside monitoring sheets :	
500 €	
• Transport of samples from local laboratories to the centralised laboratory :	200 €
• Biology analyses :	
• Cytokine assays at the rate of 6 assays per patient for 50 patients, i.e. 300 assays:	
	13 414 €
• Oxidative stress testing at a rate of 6 tests per patient for 50 patients:	
	4 500 €
• Presentation of results (conference) :	500 €

The total cost is estimated at **34,914** euros.

B. Insurance

Insofar as the research is qualified as Research in routine care by the requested CPP, which means that there is no additional risk associated with the study, the insurance will be that of the establishment responsible for the care (article L. 1142-2).

XII. Feasibility of the study

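### The allowance for patients included but not randomised multiplies by 1.2 instead of dividing by 0.8, so 60 inclusions are expected to give 48 randomised patients, not the 50 required

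*Combined protocol and SAP*

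**What the plan says.** The sample-size justification (Statistics, part B) works down in steps from 151 per group with a single assay, to 42 with a baseline measurement, and then: "the number of patients was reduced to 25 per arm". The error rates are given as follows: "The errors of the first and second kind were set at 5% and 10% respectively". The section then makes one allowance, for loss before randomisation. It begins "Taking into account an estimated 20% of patients who may have been included but not randomised", gives death and refractory shock as the reasons, and concludes that "the plan is to include 30 patients per group, i.e. a total of 60 patients".

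The loss arises because patients are included at the start of cooling but randomised only between H18 and H24. The randomisation section (headed Prize draw) explains the purpose: "This delayed randomisation will allow only patients alive at the end of the 32.5-33.5 CCT period to be randomised".

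Two other places carry the same numbers. Recruitment procedures states: "It is planned to include 60 patients admitted to the intensive care unit". The study budget is headed "Estimate based on 50 randomised patients" and costs the laboratory work on that basis: "Cytokine assays at the rate of 6 assays per patient for 50 patients, i.e. 300 assays".

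I found no provision for replacing patients who are included but not randomised, and none for continuing inclusion until 50 have been randomised.

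**The concern.** Three figures are stated: 60 included, 20% of those included lost before randomisation, and 25 per arm (50 in all) needed. They cannot all hold. Losing 20% of 60 leaves 48. Ending with 50 from 60 means losing 10 of 60, which is 16.7%.

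This is the familiar slip of inflating by 1 + d when the loss d is a share of the larger, inflated number. At stake is a little power, and the correctness of a sample-size statement that an ethics committee or reader can check in one line. The loss before randomisation is also the only loss the plan allows for, so the 60 contains no other margin that could absorb the shortfall.

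The wording adds to the confusion. Patients have no group when they are included, so 30 per group describes something that does not exist at that stage. Only the randomised patients can be counted per arm.

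**Working it through.** **Inputs** (all from Statistics, part B, unless noted)

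- Difference 15 pg/ml (115 versus 100), SD 40 pg/ml, correlation 0.85.
- Type I error 5%, type II error 10%. Sidedness is not stated; two-sided reproduces the plan's figure and one-sided does not (122 per group).
- Required: 25 per arm. Loss before randomisation: 20% of those included. Planned inclusions: 60.
- Allocation 1:1 (randomisation section). Budget basis: 50 randomised (study budget).

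**Step 1. The plan's own chain**

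- Single assay, two-sided t test: 150.4, so 151 per group. This matches.
- Baseline adjustment: 151 x (1 - 0.85²) = 41.9, so 42. This matches.
- Repeated measures: 25 is reproduced by one baseline and four follow-up measurements, with variance factor (1 + 3 x 0.85)/4 - 0.85² = 0.165, and 151 x 0.165 = 24.9, so 25. The plan does not state this factor; it is the one that returns the plan's figure.
- Inflation: 25 x 1.2 = 30 per group, 60 in total. This matches exactly.

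**Step 2. The inflation that fits the wording**

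If a share d of those included is lost, the number to include is n/(1 - d).

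- In total: 50/0.8 = 62.5, so 63.
- Rounded per arm: 25/0.8 = 31.25, so 32, or 64 in total.

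**Step 3. What 60 inclusions deliver**

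- 60 x 0.8 = 48 randomised, 24 per arm: two fewer than required.
- The loss rate at which 60 gives exactly 50 is 10/60 = 16.7%.

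**Step 4. Effect on power**

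This does not depend on how 25 was obtained. If 25 per arm gives 90% power, two-sided 5%, normal approximation, the standardised effect is 1.960 + 1.282 = 3.242. At 24 per arm it is 3.242 x √(24/25) = 3.176, and power is Φ(3.176 - 1.960) = 88.8%.

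The plan's 25 is a rounded-up number, so the power at 25 can also be computed from a variance factor. The difference is 15 and the SD is 40 x √factor:

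| Factor | Where it comes from | Power at 25 per arm (normal / t) | Power at 24 per arm (normal / t) |
|---|---|---|---|
| 0.165 | 1 baseline, 4 follow-up (returns 25) | 90.4% / 89.2% | 89.2% / 87.9% |
| 0.1775 | 1 baseline, 3 follow-up | 88.2% / 86.9% | 86.9% / 85.5% |
| 0.1575 | 1 baseline, 5 follow-up | 91.6% / 90.5% | 90.5% / 89.3% |

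The level of power moves with the factor. The cost of losing one patient per arm stays between 1.1 and 1.4 points in these rows.

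**Step 5. Chance of reaching 50 randomised**

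Assume each included patient is randomised independently with probability 0.8:

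- from 60 inclusions: 32%
- from 63 inclusions: 62%
- from 64 inclusions: 71%

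If inclusion continued until 50 were randomised, the mean number of inclusions would be 50/0.8 = 62.5, with 10th and 90th percentiles of 58 and 68.

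**The case against.** Four points can be made for the plan.

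*The 20% may have been meant as an addition to the 50 required.* The text is a translation, and pairing 60 included with 50 randomised fits that intention. This is possible, but the sentence does not say it. If it is what was meant, the sentence still needs correcting, because the loss is then 16.7% of those included. The finding survives as a fault of wording rather than of number.

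*The power figures rest on a variance factor that the plan never gives.* This is right for the 0.165 row. The six samples actually scheduled (H0, H12, H24, H32, H40, H48) allow other choices. With one baseline and five follow-up measurements, 24 per arm still gives 90.5% on the normal approximation. With three measurements before rewarming and three after, the factor is 0.097 and power at 24 per arm is about 98%. These alternatives, however, dispute the plan's 25 per arm, which is a separate matter. Taking 25 per arm at 90% as the plan states it, 24 per arm gives 88.8% whatever the factor.

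*The shortfall is within the noise.* The 20% is an unsourced estimate. The number randomised from 60 has a standard deviation of √(60 x 0.8 x 0.2) = 3.1, so a shortfall of two is less than one standard deviation. This stands, and it is why the point is minor. It does not make the stated number follow from the stated rate.

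*The budget is a cost basis, not a recruitment requirement.* This also stands. The requirement comes from the 25 per arm; the budget only shows that 50 was the number the authors had in mind.

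**Conclusion.** The concern holds and is minor. With the 20% read as written, the inclusions needed for 25 per arm are 63 (64 if rounded per arm), not 60. The stated 60 is expected to give 48 randomised patients, one fewer per arm than required, and power of 88.8% instead of the planned 90%.

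The inclusion arithmetic needs only the plan's own figures and its own wording of the loss. The power figure assumes in addition that 25 per arm gives exactly 90% with a two-sided 5% test under the normal approximation. The probabilities of reaching 50 assume independent patients and a true randomisation rate of 80%. Whether 25 per arm is itself well founded is not judged here.

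**What to change.** Choose one of two corrections to the last step of the sample-size section.

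1. Keep 60 inclusions and state what they yield. Suggested text: With 60 inclusions and 20% of them not randomised, 48 randomised patients (24 per arm) are expected, giving about 89% power (normal approximation, taking 25 per arm as giving 90%). This costs one sentence and no patients.
2. Define the target as randomised patients. Suggested text: Patients will be included until 50 have been randomised; about 63 inclusions are expected if 20% are not randomised. This adds about 3 inclusions in expectation and agrees with the budget basis of 50. It changes the enrolment rule, so the figure of 60 under Recruitment procedures must change with it.

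If the authors meant 10 patients lost for every 50 randomised, 60 can stay, but the loss should be restated as about 17% of those included.

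In every case, replace the 30 per group with the total number included, and keep per-arm counts for randomised patients.
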